## PROTOCOL SUMMARY

### 1. Objectives:

The primary objective of this study is to determine the complete response rate (negative bladder biopsy, negative urine cytology, normal exam under anesthesia) at 3 months in high risk non-invasive urothelial carcinoma of the lower urinary tract (bladder, prostatic urethra)

## [name], Phase II Study of BCG followed by Sunitinib for High risk NMIBC

patients treated with a 6-week induction course of intravesical ***bacillus Calmette-Guerin (BCG)*** followed by a 2 week rest period and 4 week course of oral **Sunitinib**.

Secondary objectives of the trial:

- a. Determine the percentage of patients with high risk non-muscle invasive urothelial carcinoma of the lower urinary tract (bladder, prostatic urethra) with a complete response (negative bladder biopsy, negative urine cytology, normal exam under anesthesia) at 6 months treated with a 6-week induction course of intravesical ***bacillus Calmette-Guerin (BCG)*** followed by a 4 week course of oral Sunitinib +/- a second course of BCG followed by Sunitinib.
- b. To assess the recurrence-free survival of patients treated with BCG followed by Sunitinib at 2 years with an intact bladder.
- c. To determine toxicity related to treatment with BCG followed by Sunitinib.

**Correlative objectives of trial:** To correlate changes in VEGF, VEGFR, p53, and other cytokine expression in the voided urine and/or serum with response in patients treated with **BCG** followed by **Sunitinib**.

### 2. Rationale:

This study is based on the concept that angiogenesis and vascular endothelial growth factor play a role in disease progression in patients with lower urinary tract non-muscle invasive urothelial carcinoma. Treatment with BCG is likely to target this pathway and consolidating treatment with Sunitinib, a VEGF receptor inhibitor may improve the complete response rate in this population which currently is approximately 45-55% at 3 months.

### 3. Primary Statistical Endpoint:

The primary endpoint of this phase II trial is to determine the complete response rate at 3 months as assessed by negative bladder biopsy, negative urine cytology, and normal exam under anesthesia of patients treated with a 6 week induction course of BCG followed by a 4-week course of **Sunitinib**.

### 4. Schedule:

Patients will receive intravesical BCG ( 50mg TICE BCG in 50 ml normal saline) once weekly for 6 weeks within 6 weeks of bladder biopsy confirming high risk non-muscle invasive urothelial carcinoma. Two weeks after completion of BCG, patients will receive Sunitinib (50 mg daily) continuously for 28 days followed by a two week rest period. Patients will be reassessed with transurethral resection and urine cytology. Those with residual/recurrent

disease will receive a second course identical to the initial protocol. Those with a complete response following initial or second treatment will be placed on maintenance BCG (3 week course every 6 months for 2 years). Those failing (progression, intolerance) initial/secondary treatments will be offered alternative therapy.

## 1. OBJECTIVES

### PRIMARY OBJECTIVE:

The primary objective of this study is to determine the complete response rate ( (negative bladder biopsy, negative urine cytology, normal exam under anesthesia) at 3 months in high risk non-invasive urothelial carcinoma of the lower urinary tract (bladder, prostatic urethra) patients treated with a 6-week induction course of intravesical ***bacillus Calmette-Guerin (BCG)*** followed by a 6 week course of oral **Sunitinib** (4 weeks on drug, 2 weeks off).

### SECONDARY OBJECTIVES OF THE TRIAL:

1. Determine the percentage of patients with high risk non-muscle invasive urothelial carcinoma of the lower urinary tract (bladder, prostatic urethra) with a complete response (negative bladder biopsy, negative urine cytology, normal exam under anesthesia) at 6 months to the study regimen
2. To assess the recurrence-free survival of patients treated with **BCG** followed by **Sunitinib** at 2 years in patients with an intact bladder.
3. To determine toxicity related to treatment with **BCG** followed by **Sunitinib**.

### Correlative objectives of trial:

To correlate changes in VEGF, VEGFR, p53, HIF1a and other cytokine expression in the voided urine, serum and/or tissue with response in patient treated with **BCG** followed by **Sunitinib**

## 2. BACKGROUND

### 2.1 NON-MUSCLE INVASIVE UROTHELIAL CARCINOMA OF THE LOWER URINARY TRACT

Approximately 67,000 people will be diagnosed with bladder cancer in 2007.[1] Most patients are initially diagnosed with non-muscle invasive bladder cancer. Non-muscle invasive urothelial cancer

## [name], Phase II Study of BCG followed by Sunitinib for High risk NMIBC

of the lower urinary tract is characterized by tumor involving the mucosa or lamina propria of the urinary bladder and/or prostatic urethra. These patients are most commonly treated with initial endoscopic resection. The natural history of non-muscle invasive urothelial carcinoma is one of frequent recurrences. The close surveillance of patients with non-muscle invasive urothelial carcinoma with repeated upper tract imaging (computed tomography, intravenous pyelogram), office cystoscopy (every 3 months initially), and urine cytology combined with the need for frequent return to the operating room for repeat endoscopic resection make bladder cancer one of the most expensive malignancies to treat per individual patient.[2]

This surveillance pattern is driven by the fact that up to 1/3 of patients will progress to more invasive disease. A multitude of both clinical and molecular factors have been studied to attempt to identify which patients are at high risk of progression.[3] To date, the two proven factors associated with risk of progression are grade and stage. Patients with high grade tumors have at least a 50% chance of recurrence. This can range from 50-90% in patients with carcinoma in situ (CIS), a flat high grade mucosal lesion. Both high grade tumors and CIS carry a high risk of progression to muscle invasive and/or metastatic disease. In addition, patients with T1 tumors (invasion into the lamina propria) have a 50-70% chance of recurrence and a high probability of progression to more invasive disease.[4] Once a patient has advanced to muscle invasive disease, they have decreased 5-year survival similar to those patients who present initially with muscle invasive urothelial carcinoma.[5] In addition, the current standard for muscle invasive bladder cancer is radical cystectomy with or without neoadjuvant chemotherapy which is associated with a 1-3% peri-operative mortality ratio, a 20-30% peri-operative complication ratio, and significant alteration in the patient's quality of life.[6, 7] Clinical efforts have focused on the prevention of recurrence and progression for patients with non-muscle invasive urothelial carcinoma.

For those patients with adverse features including tumor recurrence, multifocality, invasion into the lamina propria, sessile architecture, mixed histology, high grade tumor, or tumors associated with carcinoma in situ, endoscopic resection is typically combined with intravesical therapy. There are a variety of current intravesical agents used in the management of non-muscle invasive bladder cancer. Mitomycin is a chemotherapeutic agent that is frequently instilled at the time of endoscopic resection. In several series, mitomycin has been shown to reduce the risk of recurrence when combined with endoscopic resection.[8] However, it does not appear to prevent disease progression which is the predominant factor in overall survival in this population. As a consequence several intravesical agents are used clinically in the peri-operative period to prevent tumor recurrence and progression. To date, the most effective agent is bacillus Calmette Guerin (BCG). In several randomized controlled studies in patients with non-muscle invasive disease, the average percentage of patients with complete response to intravesical chemotherapy was roughly 30% compared to 45-55% for those treated with BCG at 3 months. While the percentage of patients responding at 3 months with CIS is similar to other tumors using intravesical chemotherapy, up to 70% of patients treated with BCG will have a complete response at 3 months.[9] An expected 30% of patients failing initial induction with BCG will respond to a second

course of BCG. However, residual disease following two induction courses of BCG denotes a high risk of tumor progression.

## 2.2 ANGIOGENESIS AND UROTHELIAL CANCER

Angiogenesis is a prerequisite to cancer growth and metastasis. It is regulated by the balance between various angiogenic and antiangiogenic factors released by cancer cells or nonmalignant cells that infiltrate the cancer [10, 11]. Microvessel density (MVD), a measure of tumor angiogenesis, has been shown to correlate with a higher incidence of metastasis and a worse prognosis in various cancers, including bladder carcinoma [12, 13]. Specifically, the development of new vasculature has been associated with progression of urothelial cancer from superficial to muscle invasive disease [14]. Canoglu et al [15] looked at tumor specimens from 77 patients with bladder cancer. They found MVD to correlate with tumor grade, stage and prognosis. Significantly higher MVD was shown in invasive tumors compared to superficial tumors ( $p < 0.05$ ). MVD was also shown to increase with tumor grade and stage ( $p < 0.05$ ) and, high MVD was correlated with risk of clinical progression in both superficial and invasive bladder carcinomas ( $p < 0.05$ ,  $p < 0.001$ ) respectively.

Additional support for angiogenesis in the development and progression of urothelial carcinoma has been shown by way of angiogenic factors and their receptors. Tyrosine-kinase receptors, including many growth factor receptors such as the receptors for fibroblast growth factor (FGF), epidermal growth factor (EGF), vascular endothelial growth factor (VEGF), platelet-derived endothelial cell growth factor (PDGF) and Her2/neu, have been found over expressed in tissue, serum, and urine of patients with bladder cancer [16-18]. For many of these growth factor receptors, the degree of expression has been associated with the progression of cancer and a poor prognosis [19]. Several investigators have reported a positive association between over-expression of EGFR and high-grade, high-stage bladder cancer; identifying the receptor as an independent prognostic factor in patients with advanced bladder cancer by some, but not all investigators [20-23].

Of the angiogenic factors, VEGF has been identified as a crucial regulator of both normal and pathologic angiogenesis. VEGF produces a number of important biologic effects including endothelial mitogenesis and migration, extracellular matrix remodeling via induction of proteinases, increased vascular permeability and maintenance of newly formed vasculature [24]. VEGF exerts its biologic effects through the binding and stimulation of two receptors on the surface of endothelial cells: Flt-1 and KDR. Increased VEGF expression has been measured in most human tumors including those of the bladder [25-27]. In addition to the high expression rate, several investigators have reported a correlation of VEGF expression to higher stage, progression and prognosis in bladder cancers. With the progression of tumor grade and clinical stage, the positive rate of VEGF gene expression significantly increased [26-28]. Serum VEGF levels appear to be significantly associated with tumor stage, grade, vascular invasion and carcinoma in situ.

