##### *Clinical Safety and Efficacy*

The estimated response rate for patients with high risk non-invasive disease is approximately 50% with patients with isolated carcinoma in situ experiencing response rates of 70%. Based on several randomized controlled trials performed by the Southwest Oncology Group in the early 1990s,

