Urine represents an ideal medium to evaluate response to therapy in patients with localized bladder cancer as it may directly indicate the response to therapy. Further, based on preliminary results described previously, serum levels of biomarkers may also be informative. We will investigate the effect of BCG and sunitinib therapy on urinary and serum levels of various VEGFs, soluble VEGF receptors, and cytokines IL8, IL6, interferon gamma, and interferon alpha. Measurements will be performed using commercially-available ELISA kits. Utility of additional biomarkers (e.g., PDGF, [35]) will be evaluated on a pilot basis.

Correlation of changes in VEGF, VEGFR, p53, and other cytokine expression to response will be explored. Markers will be grouped based on terciles of the distribution. Bivariate relationships between the expression level and response status will be assessed with the Mantel-Haenszel chi-square test. Logistic regression will be used to assess the effect of combining markers to predict response. Differences in time to recurrence by expression level will be illustrated by Kaplan-Meier plots and tested using the log-rank test. Due to the sample size and the number of factors we will be statistically testing, these analyses will be considered exploratory until confirmed in a larger, independent, clinical trial.

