### 16.2 ANALYSES

The primary endpoint for this study will be the complete response rate. This rate will be reported along with 95% confidence intervals.

This study has several secondary endpoints. Response rates at 6 months will be reported with 95% confidence intervals for patients with an intact bladder. Kaplan-Meier estimates will be used to describe recurrence-free survival, including 2-year recurrence-free survival estimates. Toxicity of this therapy will be described, both overall and by grade. Toxicity rates will be tabulated by type and category.

Correlation of changes in VEGF, VEGFR, p53, and other cytokine expression to response will be explored. Markers will be grouped based on terciles of the distribution. Bivariate relationships between the expression level and response status will be assessed with the Mantel-Haenszel chi-square test. Potential analyses will include logistic regression with an outcome of response and Kaplan-Meier methods for time to recurrence. Differences in time to recurrence by expression level will be illustrated by Kaplan-Meier plots and tested using the log-rank test. Due to the sample size and the number of factors we will be statistically testing, these analyses will be considered exploratory until confirmed in a larger, independent, clinical trial.

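### The planned marker-response test takes no account of carcinoma in situ, so for serum VEGF level an association with response could partly restate what the entry pathology already shows

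*Combined protocol and SAP*

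**What the plan says.** The correlative objective in the Protocol Summary is "To correlate changes in VEGF, VEGFR, p53, and other cytokine expression in the voided urine and/or serum with response". Section 1 repeats it and adds HIF1a and tissue.

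The analysis paragraph in section 16.2, repeated in large part in section 12.0, opens on the same scale: "Correlation of changes in VEGF, VEGFR, p53, and other cytokine expression to response will be explored". It continues "Markers will be grouped based on terciles of the distribution", and then "Bivariate relationships between the expression level and response status will be assessed with the Mantel-Haenszel chi-square test". No stratification factor or clinical covariate is named. On regression, section 12.0 says "Logistic regression will be used to assess the effect of combining markers to predict response", and section 16.2 says "Potential analyses will include logistic regression with an outcome of response and Kaplan-Meier methods for time to recurrence". Neither lists CIS or stage. Both sections call the analyses exploratory, giving sample size and the number of factors as the reasons.

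The background supplies two further facts. Section 2.2 says "Serum VEGF levels appear to be significantly associated with tumor stage, grade, vascular invasion and carcinoma in situ". Section 2.3, under Clinical Safety and Efficacy, puts response in high-risk disease at about 50%, "with patients with isolated carcinoma in situ experiencing response rates of 70" percent. Section 2.1 gives 45-55% on BCG at 3 months and up to 70% in CIS.

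Sections 3.1.3 and 3.1.4 admit patients with and without CIS, at stage T1 or lower, all of them high grade.

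**The concern.** A variable related to both the marker and the outcome will link them in an unadjusted test. By the protocol's own account CIS is such a variable for serum VEGF level: it is associated with the level, and it responds to BCG more often. If patients with CIS gather in one end tercile, that tercile shows a different response rate even if VEGF plays no part.

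What is at stake is interpretation. Sections 2.6 and 12.0 want markers that help predict response, and section 2.6 wants them to guide the choice between intravesical and more aggressive treatment. CIS is on the entry pathology report, so a marker that only stands in for it adds nothing to that choice.

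The test sentence compounds this. It refers to expression level, whereas the objective and the lead sentence refer to changes. The association in section 2.2 concerns levels.

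**Working it through.** **The plan's own figures.** None is given for the marker tests. The sample size comes from the two-stage design (16 of 24, then 25 of 36; 55% versus 75%), which reproduces: exact type I error 0.0493 (stated 4.9%) and power 0.8012 (stated 80%).

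**Inputs from the documents.** 36 patients, three terciles of 12, response 70% with CIS. For patients without CIS no rate is given; I use 45% and 50%, from the 45-55% range.

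**Assumptions, not in the documents.** CIS share 25% or 50%. Marker normally distributed, and 0 to 1.5 SD higher in CIS (section 2.2 gives neither size nor direction). Given CIS status, the marker has no effect on response.

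**Tests, two-sided 5%.**
- Unstratified, as planned: Q = (N − 1)r², where r is the correlation of tercile score with response (0/1), referred to chi-square on 1 df.
- Stratified by CIS: Q = [Σ(O − E)]² / ΣV. Within each stratum O − E is the sum of score × response minus its expectation, and V = SxxSyy/(n − 1).

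**Hand check of the mechanism** (CIS 50%, response 70% versus 50%, shift 1 SD). The upper tercile cut c solves 0.5[1 − Φ(c)] + 0.5[1 − Φ(c − 1)] = 1/3, so c = 0.988. The CIS share of the top tercile is 0.5 × 0.505 / 0.333 = 0.757, and its expected response is 0.50 + 0.20 × 0.757 = 0.651. By symmetry the bottom tercile has CIS share 0.243 and response 0.549. A marker with no effect thus shows about 55%, 60% and 65% across terciles.

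**Rejection rates for a marker with no effect of its own** (N = 36, 40,000 trials per setting):

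| CIS share | Response without CIS | No shift | 0.5 SD | 1 SD | 1.5 SD | Stratified by CIS, all shifts |
|---|---|---|---|---|---|---|
| 25% | 45% | 6.3% | 7.2% | 9.0% | 11.6% | 4.8-5.2% |
| 25% | 50% | 6.3% | 6.6% | 7.9% | 9.7% | 4.9-5.1% |
| 50% | 45% | 6.2% | 7.8% | 11.2% | 16.0% | 4.8-5.1% |
| 50% | 50% | 5.9% | 6.8% | 9.2% | 11.9% | 4.8-5.2% |

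For shifts of 0.5 to 1.5 SD the range is 6.6 to 16.0%. The mean difference in response between top and bottom terciles runs from 3.8 points (57.1 − 53.3) to 17.6 points (66.3 − 48.7). With 55% response outside CIS, rejection is 6.1 to 9.0%. With 24 patients and 45-50% outside CIS, it is 7 to 13%.

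The fair comparator is the no-shift column, about 6%, rather than the nominal 5%: part of the excess at small shifts is the behaviour of the test at this sample size.

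**Stage acting the other way.** Suppose half the patients are T1, T1 raises the marker as much as CIS does, and T1 lowers response. With a 20-point lower response the unstratified rate falls back to about 6 to 7%; a 10-point one offsets the bias in part. The documents give no response rate by T1, so this too is an assumption.

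**Cost of stratifying when there is nothing to adjust for** (an assumed real marker effect, marker unrelated to CIS, 4,000 trials): power 58.7% versus 54.9% at 25% CIS, and 57.2% versus 54.1% at 50% CIS. The losses are 3.8 and 3.1 points.

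**The case against.** **The analyses are labelled exploratory, and no decision rule uses them.** This stands, and it limits the weight of the point. It does not remove it. The stated reasons are sample size and number of factors, and a larger trial eases the first while confounding grows more visible. With CIS 50%, response 70% versus 50% and a 1 SD shift, rejection rises from roughly 8 to 9% at 36 patients to 13% at 100 and 23% at 200. A larger trial using the same unadjusted test would tend to confirm the artefact.

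**A stand-in for CIS still predicts response.** True. The error lies only in reading it as information beyond entry pathology.

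**The plan means change, not level.** The lead sentence does say changes, so the wording is ambiguous rather than settled on level. Nothing in the documents ties change to CIS. If change is what is tested, the evidence for confounding weakens and stratification becomes a safeguard.

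**The 70% is for isolated CIS.** Section 2.3 says so, and section 2.1 says up to 70%. No rate is given for papillary tumours with concomitant CIS, so a present/absent stratum may separate response less sharply than simulated.

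**Logistic regression is planned.** It combines markers in section 12.0 and is only potential in section 16.2. Clinical covariates are not excluded, but none is planned.

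A reader might also infer that grade confounds the test, since section 2.2 names it. It can hardly do so here, because every patient has high-grade disease.

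**Conclusion.** The point holds for serum VEGF level and the Mantel-Haenszel test of response. As planned, the test cannot separate an effect of the marker from CIS status. Its false-positive rate is about 7 to 16% under the assumed CIS shares and shifts, against about 6% with no shift and about 5% when stratified. The upper end needs 50% CIS, 45% response without CIS and a 1.5 SD shift. Because stage could act against CIS, the documents do not settle the net direction.

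Three wider readings are not supported:
- That all markers are affected. Section 2.2 makes the statement for serum VEGF only, not for urine markers, soluble receptors, cytokines, p53 or HIF1a.
- That the log-rank test of time to recurrence is biased in the same way. Section 2.1 gives overlapping recurrence ranges, 50-90% for CIS and 50-70% for T1, so no direction follows, and no size was computed.
- That the trial's conclusion is at risk. The primary complete response rate and the two-stage rule do not use the markers.

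This is an inexpensive improvement to an exploratory objective, not a defect in the main design.

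**What to change.** In sections 12.0 and 16.2:

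1. Report the Mantel-Haenszel test stratified by CIS at entry (present/absent) beside the planned unadjusted test. State that a marker will be described as adding information beyond entry pathology only if the stratified result supports it. Stratifying by CIS does not deal with stage, so the report should say so.
2. For urine and serum markers, make the tested quantity the within-patient change, for example a log ratio: Week 12 versus Week 8 for sunitinib, and Week 6 versus Week 1 for BCG where drawn. The study calendar already schedules these samples, though the Week 1 and Week 6 samples are waived when BCG is given locally. The renal cell studies cited in section 12.0 also worked with change over a dosing cycle.
3. For tissue markers such as p53 and HIF1a, keep the level. Study tissue is collected only at the 3-month biopsy, so no change can be computed.

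The cost is wording only: no added patients, samples or pathology. If CIS is unrelated to the marker, the stratified test gives up about 3 to 4 points of power. At a 25% CIS share there would be about 9 patients with CIS (0.25 × 36), or about 3 per tercile, so estimates within that stratum will be imprecise. The wording should be settled before marker data are analysed.
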